15. PUBLICATION OF STUDY RESULTS

15.1. Communication of Results by Pfizer

Pfizer fulfills its commitment to publicly disclose clinical trial results through posting the results of studies on www.clinicaltrials.gov (ClinicalTrials.gov), the European Clinical Trials Database (EudraCT), and/or www.pfizer.com, and other public registries in accordance with applicable local laws/regulations.

In all cases, study results are reported by Pfizer in an objective, accurate, balanced, and complete manner and are reported regardless of the outcome of the study or the country in which the study was conducted.

www.clinicaltrials.gov

Pfizer posts clinical trial US Basic Results on www.clinicaltrials.gov for Pfizer-sponsored interventional studies (conducted in patients) that evaluate the safety and/or efficacy of a Pfizer product, regardless of the geographical location in which the study is conducted. US Basic Results are submitted for posting within 1 year of the primary completion date (PCD) for studies in adult populations or within 6 months of the PCD for studies in pediatric populations.

PCD is defined as the date that the final subject was examined or received an intervention for the purposes of final collection of data for the primary outcome, whether the clinical study concluded according to the prespecified protocol or was terminated.

EudraCT

Pfizer posts European Union (EU) Basic Results on EudraCT for all Pfizer-sponsored interventional studies that are in scope of EU requirements. EU Basic Results are submitted for posting within 1 year of the PCD for studies in adult populations or within 6 months of the PCD for studies in pediatric populations.

www.pfizer.com

Pfizer posts Public Disclosure Synopses (clinical study report synopses in which any data that could be used to identify individual patients has been removed) on www.pfizer.com for Pfizer-sponsored interventional studies at the same time the US Basic Results document is posted to www.clinicaltrials.gov.

15.2. Publications by Investigators

Pfizer supports the exercise of academic freedom and has no objection to publication by the principal investigator (PI) of the results of the study based on information collected or generated by the PI, whether or not the results are favorable to the Pfizer product. However, to ensure against inadvertent disclosure of confidential information or unprotected inventions, the investigator will provide Pfizer an opportunity to review any proposed publication or other type of disclosure of the results of the study (collectively, "publication") before it is submitted or otherwise disclosed.

The investigator will provide any publication to Pfizer at least 30 days before it is submitted for publication or otherwise disclosed. If any patent action is required to protect intellectual property rights, the investigator agrees to delay the disclosure for a period not to exceed an additional 60 days.

The investigator will, on request, remove any previously undisclosed confidential information before disclosure, except for any study- or Pfizer product-related information necessary to the appropriate scientific presentation or understanding of the study results.

If the study is part of a multicenter study, the investigator agrees that the first publication is to be a joint publication covering all investigator sites, and that any subsequent publications by the PI will reference that primary publication. However, if a joint manuscript has not been submitted for publication within 12 months of completion or termination of the study at all participating sites, the investigator is free to publish separately, subject to the other requirements of this section.

For all publications relating to the study, the institution will comply with recognized ethical standards concerning publications and authorship, including Section II - "Ethical Considerations in the Conduct and Reporting of Research" of the Uniform Requirements for Manuscripts Submitted to Biomedical Journals, http://www.icmje.org/index.html#authorship, established by the International Committee of Medical Journal Editors.

Publication of study results is also provided for in the CSA between Pfizer and the institution. In this section entitled Publications by Investigators, the defined terms shall have the meanings given to them in the CSA.

If there is any conflict between the CSA and any attachments to it, the terms of the CSA control. If there is any conflict between this protocol and the CSA, this protocol will control as to any issue regarding treatment of study subjects, and the CSA will control as to all other issues.

1. VERSION HISTORY

This Statistical Analysis Plan (SAP) for study B1851178 is based on protocol amendment 1 dated 19JAN2018. The study protocol was amended on 19 February 2019. The main purpose of this SAP amendment is to ensure the consistency between protocol amendment 2 and the SAP.

SAP Version	Change	Rationale
1	Not Applicable	Not Applicable
2	Add GMFR analyses compare between Cohorts of children 7 months to < 6 years of age (Cohort 2, 3,4) and Cohort of infants 6 weeks to 2 months of age (Cohort 1), and analyses to address Center for Drug Evaluation (CDE) requests	Protocol Amendment 2
3	Section 2. Add statement to include the additional 280 subjects into analyses	Request by regulatory authorities

Table 1. Summary of Major Changes in SAP Amendments

2. INTRODUCTION

This SAP provides the detailed methodology for summary and statistical analyses of the data collected in study B1851178. This document may modify the plans outlined in the protocol; however, any major modifications of the primary endpoint definition or its analysis will also be reflected in a protocol amendment. An additional 280 subjects stated in protocol amendment 2 will be analyzed similarly to that of the original 280 subjects enrolled from town level immunization clinics which were under the Huaiyin county Center for Disease Control (CDC). Analyses for primary study report will include data collected from originally enrolled subjects including 280 subjects from town level immunization clinics, this may be repeated with study data from originally enrolled subjects from town level CDC replaced with these additional subjects.

In response to the request that was provided to Study B1851178 team by Center for Drug Evaluation (CDE) of China National Medical Products Administration (NMPA) on 22 November 2021 about age expansion NDA, the study team was requested to include the 280 additional subjects stated in protocol amendment 2 into the analyses outlined in this SAP.

Among the 280 additional subjects, a total of 177 subjects were enrolled into Cohort 2, 73 subjects were enrolled into Cohort 3 and 30 subjects were enrolled into Cohort 4. All study endpoints, analysis sets, statistical analyses and summaries defined in this SAP had been performed for the primary study report and these will be repeated again by including the additional 280 subjects in to Cohorts 2-4 as a supplemental study report.

PFIZER CONFIDENTIAL
Page 6

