Amendment 2	endment 2 07 February 2019	 Protocol Summary, Section 1.2, Section 3.4, Section 7.5.1, Section 7.5.2, Section 9.4: Added the enrollment of additional 280 subjects from county CDCs. Rationale: To provide additional data in the event that only subjects recruited at municipal and county level CDCs should be included in vaccine clinical studies.
		- Section 3.4: Change "Randomized subjects withdrawn from the study will not be replaced, regardless of the reason for withdrawal" to "Randomized subjects who withdraw from the study may be replaced to maintain adequate numbers to achieve study objectives". Rationale: May need to recruit additional subjects due to higher than expected subject withdrawal in order to achieve study objective.
		 Section 7.5.2: Delete "13vPnC" from "the blood samples taken before vaccination and 1 month after the last 13vPnC vaccination in each of the 3 cohorts" in Cohorts 2, 3, 4. Rationale: Added

Document	Version Date	Summary of Changes and Rationale
		specificity and clarity.
		- Section 6.1.1, Section 6.2.1, Section 6.3.1, and Section 6.4.1: Change "including date of birth, sex and race" into "including full date of birth, sex and race. The date of birth will be collected to critically evaluate the immune response and safety profile by age". Rationale: Added specificity and clarity.
		- References: Updated to reflect changes.
		- Appendix 1: Added CDC in the abbreviation table.

This amendment incorporates all revisions to date, including amendments made at the request of country health authorities and institutional review boards (IRBs)/ethics committees (ECs).

TABLE OF CONTENTS

LIST OF TABLES	10
APPENDICES	11
PROTOCOL SUMMARY	12
STUDY DESIGN.	13
Description	13
STATISTICAL ANALYSIS	14
Immunogenicity Analysis Populations	14
Safety Analysis	14
Analysis Timing:	14
SCHEDULE OF ACTIVITIES	15
1. INTRODUCTION	19

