Appendix 1. Abbreviations

PROTOCOL SUMMARY

This study is designed to support licensure of 13-valent Pneumococcal Conjugate Vaccine (13vPnC) through 5 years of age.

This study includes 4 separate cohorts broken down by age. Cohort 1 will include infants 6 weeks to 2 months of age that will be vaccinated with 13vPnC according to the currently licensed infant schedule (2, 4, 6 and 12 to 15 months). Cohorts 2, 3 and 4 range in age from 7 months to 5 years of age (Cohort 2 - 7 months to <12 months of age; Cohort 3 - \geq 1 year to <2 years; Cohort 4 - \geq 2 years to <6 years of age). These three cohorts are of primary interest in obtaining licensure in the 15 month to 5 year age range and addressing the Center for Drug Evaluation (CDE) request to obtain data in this age group. Immune responses before and after the last vaccination in each of these age groups will be measured and used as a surrogate of efficacy. Post vaccination serotype specific serum anticapsular immunoglobulin G (IgG) responses in Cohorts 2, 3, and 4 will be compared to the post infant series responses in Cohort 1 as a bridge to efficacy. Cohorts 2, 3, and 4 will also include a control group vaccinated with *Haemophilus influenzae* type b (Hib) vaccine. The Hib vaccinated infants and children will serve as controls for assessment of the safety and immunogenicity of Cohorts 2, 3, and 4. In addition to serving as a bridge to efficacy for Cohorts 2, 3, and 4, Cohort 1 will provide the antibody persistence data at 12, 24, 36 and 48 months after the last vaccination required by the CDE.

An additional 280 subjects will be recruited because during the conduct of the study, 280 subjects were enrolled from town level immunization clinics which were under the Huaiyin county Center for Disease Control (CDC). Based on the China Vaccine Good Clinical Practice (GCP) guidelines it is unclear if town level immunization clinics are allowed to be included as clinical trial sites under the China regulations. In the review of procedures and data from subjects in the study there were no issues identified with regards to subject safety, data quality, or integrity.

Pri	mary Objective (Immunogenicity):	Pri	imary Endpoints (Immunogenicity):

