In addition to serving as a bridge to efficacy for Cohorts 2, 3, and 4, Cohort 1 will provide the antibody persistence data at 12, 24, 36 and 48 months after the last vaccination required by the CDE.

During the conduct of the study at the Huaiyin county CDC, 280 subjects were enrolled from town level immunization clinics which were under the Huaiyin county CDC. According to the China Vaccine GCP guidelines²¹ it is unclear if town level immunization clinics are allowed under the China regulations to be included as clinical trial sites. In reviewing the procedures and data from subjects in the study there were no issues identified with regards to subject safety, data quality, or integrity. An additional 280 subjects will be recruited. The purpose of enrolling these additional 280 subjects is to mitigate the possible risk that the previous 280 enrolled subjects from the town level immunization clinics will not be able to support approval/licensure of 13vPnC for infants and children 7 months through 5 years of age. All additional subjects (total 280) will follow the same study procedures and analyses.

Additional information for this compound may be found in the single reference safety document (SRSD), which for this study is the Investigator Brochure. The SRSD for the Hib vaccine is the local package insert.

Primary Objective (Immunogenicity):Primary Endpoints (Immunogenicity):• To assess the immune responses to the 13
pneumococcal serotypes induced by 13vPnC in
infants and children 7 months to <6 years of age
(Cohorts 2, 3, and 4) compared to immune
responses in infants 6 weeks to 2 months of age
(Cohort 1).• The serotype-specific IgG geometric mean
concentrations (GMCs) for each of the
pneumococcal serotypes measured 1 month after
the last dose of 13vPnC in Cohort 2, 3, 4
compared to IgG GMCs measured 1 month after
the infant series in Cohort 1.

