3.4. Approximate Number of Subjects

Approximately 656 Chinese subjects will be randomized in four different age cohorts (Cohorts 1, 2, 3, and 4 with N=125, 177, 177, and 177 respectively).

An additional 280 subjects (177 subjects of Cohort 2, 73 subjects of Cohort 3, and 30 subjects of Cohort 4) will be enrolled from county CDCs.

There will be at least 1 coordinating center which may coordinate the study activities of multiple enrolling sites. Randomized subjects who withdraw from the study may be replaced to maintain adequate numbers to achieve study objectives.

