9.4. Analysis Timing

The primary analysis will be performed when the following data are available:

- IgG immunogenicity data 1 month after the infant series in Cohort 1;
- IgG immunogenicity data 1 month after the last dose of 13vPnC in Cohorts 2, 3, 4;
- Safety data up to 6 months after the last study vaccination for Cohorts 2, 3 and 4.

In addition, the OPA data 1 month after the infant series in Cohort 1 and 1 month after the last dose of 13vPnC in Cohorts 2, 3, 4 will be included in the primary analysis if the data is available from NIFDC, at the time of the primary analysis. If the OPA data is not available at the time of the primary analysis it will be reported when it becomes available.

The above data will be summarized in the primary study report and will be submitted to regulatory authorities to support licensure of 13vPnC in infant and children 15 months to 5 years of age. Type I error of the study will all be spent for this primary analysis. In addition, supplemental summaries of immunogenicity and safety data may be generated to support renewal of the 13vPnC license.

Additionally, other data from the study that were not included in the primary report for 13vPnC licensure for infants and children 15 months to 5 years and summary reports for the 13vPnC renewal package will be analyzed and reported separately once all subjects have completed the study and all data are available. No changes to the study design or conduct of the study are intended to be made based on these results. The study will continue for the remaining subjects regardless of the results submitted to the regulatory authorities. The additional 280 subjects will be analyzed when data becomes available.

All analyses included in the final study report will be purely descriptive; therefore, no type I error adjustment is needed.

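### Does the SAP need a firm commitment to the analysis that replaces the town-clinic children with the additional 280?

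*SAP*

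**What the plan says.** **Why the additional children were enrolled.** The Protocol Summary records that "it is unclear if town level immunization clinics are allowed to be included as clinical trial sites". Protocol Section 1.2 gives the purpose of recruiting 280 more as "to mitigate the possible risk that the previous 280 enrolled subjects from the town level immunization clinics will not be able to support approval/licensure". The Amendment 2 rationale puts it as providing data "in the event that only subjects recruited at municipal and county level CDCs should be included in vaccine clinical studies". Section 3.4 gives their distribution: "An additional 280 subjects (177 subjects of Cohort 2, 73 subjects of Cohort 3, and 30 subjects of Cohort 4". None are in Cohort 1.

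**What will be analysed.** SAP Section 2 describes three analyses:

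- The primary study report, on the originally enrolled children including the 280 from town clinics. This is a commitment, and the section says it had already been performed.
- A repeat with the town-clinic children exchanged for the additional ones: "this may be repeated with study data from originally enrolled subjects from town level CDC replaced with these additional subjects". This is optional.
- A supplemental report: "these will be repeated again by including the additional 280 subjects in to Cohorts 2-4 as a supplemental study report". This is a commitment. It follows a regulatory request of 22 November 2021, under which "the study team was requested to include the 280 additional subjects stated in protocol amendment 2 into the analyses outlined in this SAP".

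Protocol Section 9.4 adds only that "The additional 280 subjects will be analyzed when data becomes available". It assigns all type I error to the primary analysis, as does SAP Section 7.2.

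**The concern.** The exchange of children is the reason for Amendment 2, yet it is the only one of the three analyses left optional. The SAP does not tie it to a regulatory decision, name who decides, or say how many town-clinic children are in each cohort. Neither committed report drops a child because of clinic type, and pooling only dilutes the contested group.

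If the authority refused the town-clinic data, no committed comparison with Cohort 1 would be clearly free of them. In the extreme case where every original Cohort 2 child came from a town clinic, Cohort 2 would have no uncontested result in either committed report.

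**Working it through.** **1. The plan's own figures.** Inputs are Protocol Section 9.5 and Tables 12-14: one-sided 2.5% test, GMR margin 0.5 (ln 2 = 0.693), 100 evaluable 13vPnC children per cohort, 2:1 allocation, and nonevaluable rates of 20% (Cohort 1) and 15% (Cohorts 2-4).

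- Randomized numbers: 100/0.80 = 125; 150/0.85 = 176.5, rounded up to 177.
- Power per serotype comes from the noncentral t with noncentrality (0.693 + difference) / [SD × √(1/n₁ + 1/n₂)] and n₁ + n₂ − 2 degrees of freedom.
- Example, Cohort 4, serotype 14: (0.693 − 0.124) / [1.257 × √(2/100)] = 3.20, power 0.890, as in Table 14.
- The product over 13 serotypes is 0.990, 0.995 and 0.887 for Cohorts 2, 3 and 4. All three match the protocol.

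**2. How much contested data the committed reports hold.** Planned Cohorts 2-4 total 3 × 177 = 531, or 531 + 280 = 811 when pooled. The documents do not give the town-clinic split by cohort, so a range is needed.

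| Town-clinic children in Cohort 1 (assumed) | Share of Cohorts 2-4, primary | Share, pooled |
|---|---|---|
| 0 | 280/531 = 53% | 280/811 = 35% |
| 125 (all of Cohort 1) | 155/531 = 29% | 155/811 = 19% |

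**3. What replacement would deliver.** Evaluable 13vPnC children = (177 − town-clinic + additional) × 2/3 × 0.85. Cohort 1 is held at 100 evaluable, so these rows assume that it loses no one.

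| Assumed town-clinic split (Cohorts 2/3/4) | Cohort sizes after replacement | Evaluable 13vPnC | Power, all 13 serotypes |
|---|---|---|---|
| 177/73/30 | 177, 177, 177 | 100, 100, 100 | 0.990, 0.995, 0.887 |
| 93/93/94 | 261, 157, 113 | 148, 89, 64 | 0.997, 0.992, 0.785 |

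In the second row, Cohort 2 is 177 − 93 + 177 = 261, Cohort 3 is 177 − 93 + 73 = 157, and Cohort 4 is 177 − 94 + 30 = 113. The Cohort 4 loss comes mostly from serotype 14, where power falls from 0.890 to 0.803.

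The additional group has the same total as the contested one, and its Cohort 2 part equals the full planned Cohort 2. That suggests child-for-child matching by cohort, as in the first row. This is an inference; no section states it.

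**4. Is the optional analysis undefined?**

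- *Set:* the SAP sentence says who leaves and who enters. The criteria in SAP Sections 4.1, 4.2 and 4.5 then apply unchanged, and Protocol Section 1.2 says the additional children follow the same procedures and analyses.
- *Circumstance:* stated in Protocol Section 1.2 and in the Amendment 2 rationale, though not repeated in the SAP.
- *Authority to run it:* SAP Section 7.1 allows analyses in support of regulatory interactions.
- *Timing:* SAP Section 2 says the primary analyses had been performed, so any new wording would also post-date those results.

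**The case for a change.** The strongest case for a change is that a contingency which justified enrolling 280 children deserves a committed analysis, and that a few lines of text and one rerun of existing programs would supply it. The regulator's request was to include the additional children; nothing in the documents says that the town-clinic data were accepted. The effect of replacement also depends on an unstated split: Cohort 4 power is 0.887 under one and 0.785 under another. Any town-clinic children in Cohort 1 could not be replaced at all.

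What stands is narrow. The SAP does not link the optional analysis to its circumstance, and it omits the counts by cohort. The counts are facts about children already enrolled, so an analyst can read them from the site records. Writing them into the SAP would alter no result.

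The rest is weaker. Dropping the town-clinic children without replacing them would empty Cohort 2 under the 177/73/30 split, but no one plans that, since replacements exist. Letting the replacement analysis carry the non-inferiority conclusion would give it a confirmatory role after all type I error has been spent. Separate GMRs by source in the pooled report would be informative, but that is a reporting choice.

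**Conclusion.** No change to the plan follows. This is a gap in detail that analysts would fill sensibly. Carrying out the plan as written gives no wrong result: the primary report stays as specified, and the pooled report answers the regulator's request. If town-clinic data were refused, the sponsor would have every reason to run the replacement analysis that the SAP already names. The Protocol Summary and Section 1.2 report no safety, data-quality or integrity problem at those clinics, so the doubt is about regulatory eligibility and not about demonstrated bias.

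The contested share could be as high as 53% of Cohorts 2-4 in the primary report and 35% in the pooled one, which explains why the point draws attention. Replacement keeps the planned power of 99.0%, 99.5% and 88.7% if the additional children mirror the town-clinic children by cohort. The lower Cohort 4 figure of 78.5% rests on an assumed near-equal split. Both rows assume 100 evaluable Cohort 1 children. Firmer wording would not alter the endpoint, margin, primary population or sample size, and it could not restore pre-specification.

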2.1. Study Objectives

2.1.1. Primary Immunogenicity Objective

• To assess the immune responses to the 13 pneumococcal serotypes induced by 13-valent pneumococcal conjugate vaccine (13vPnC) in infants and children 7 months to <6 years of age (Cohorts 2, 3, and 4) compared to immune responses in infants 6 weeks to 2 months of age (Cohort 1).

2.1.2. Primary Safety Objective

• To evaluate the safety profile of 13vPnC in infants and children 7 months to <6 years of age (Cohorts 2, 3, and 4) as measured by the incidence rates of local reactions, systemic events (including the use of antipyretic medication), and adverse events (AEs).

